## 8.0 Efficacy Assessment

### 8.1 Definitions

Response and progression will be evaluated in this study using the new international criteria proposed by the Response Evaluation Criteria in Solid Tumors (RECIST) Committee [JNCI 92(3):205-216, 2000]. Changes in only the largest diameter (unidimensional measurement) of the tumor lesions are used in the RECIST criteria. Note: Lesions are either measurable or non-measurable using the criteria provided below. The term "evaluable" in reference to measurability will not be used because it does not provide additional meaning or accuracy

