#### 8.1.3 Target lesions

All measurable lesions up to a maximum of five lesions per organ and 10 lesions in total representative of all involved organs should be identified as target lesions and recorded and measured at baseline. Target lesions should be selected on the basis of their size (lesions with the longest diameter) and their suitability for accurate repeated measurements (either by imaging techniques or clinically). A sum of the longest diameter (LD) for all target lesions will be calculated and reported as the baseline sum LD. The baseline sum LD will be used as reference by which to characterize the objective tumor response.

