### 8.3 Response Definitions:

**Complete Response (CR).** Disappearance of all evidence of tumor for at least one cycle of therapy (four weeks). Bone lesions must have improved by scan and shown complete reossification by x-ray. The patient must be free of all symptoms of cancer. Markers must be normal.

**Partial Response (PR).** 30% or greater decrease in the sum of the products of diameters of all measured lesions persisting for at least one cycle of therapy or 4 weeks. Non-measurable, but evaluable, lesions must decrease by at least 30%. No lesion may increase in size and no new lesion may appear. Bone lesions must have improved by scan and shown some reossification by x-ray. Markers must have improved.

**Minor Response (MR).** A measurable decrease in measurable lesion(s), which is too small or too brief to qualify as a Partial Response. MR is considered a failure, but should be noted as a possible signal of biologic activity.

**Progressive Disease (PD).** Any increase of  $\geq 25\%$  in the sum of the products of diameters of any measurable lesion or in estimated size of non-measurable lesions or appearance of an unequivocally new lesion. Patients should have received at least two cycles of therapy before a designation of progression is made. An increase of 50% or development of unequivocally new lesions between the first and second cycle will be considered progression without repeat measurements.

**No Change (NC).** No change in tumor size, or  $<25\%$  increase in size.

MR and PD are considered failures.

Development of a new brain lesion will be considered progressive disease.

**Confirmation of Response.** To be assigned a status of PR or CR, changes in tumor measurements must be confirmed by repeat assessments that should be performed 4 weeks after the criteria for response are first met. In the case of SD, follow-up measurements must have met the SD criteria at least once after study entry at a minimum interval of 8 weeks.

**Response and Survival Durations.** The survival of patients will be measured from entry into protocol. Duration of response will be measured from first observation of the response until progression of disease.

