## 13.0 Statistical Methods

The major trial objective is to assess the efficacy of a regimen, which adds Imatinib Mesylate to Letrozole for the first-line treatment of metastatic breast cancer. A maximum of 45 patients will be accrued at MDACC at an expected rate of 2 patients per month, taking into consideration recent historical experience for this category of patients. The accrual period should thus be completed within 24 months. The maximum sample size of 45 patients will provide an estimate of ORR with 90% credibility interval (assuming targeted rate of 40%) of width 0.24. The final analysis will also report a summary of time to disease progression, any toxicities observed during treatment, and separate estimates of objective response rate (ORR) by type and extent of prior chemotherapy. All patients who receive any dose of therapy will be included in assessments of all outcomes, with patients removed from trial for any reason counted as failures in computing ORR.

Further investigation of Imatinib Mesylate is warranted only if its addition can substantially improve the efficacy of Letrozole alone. In a large randomized trial, single-agent Letrozole resulted in objective responses in 136 of 453 patients (30%). The trial will be monitored using a Bayesian method and with cohorts of size 15; termination will be recommended if there is strong evidence that ORR is unlikely to be more than 10% greater than with Letrozole alone. (Formally, the trial will be terminated after 15 or 30 patients if  $\Pr[\text{ORR (Letrozole + Imatinib Mesylate)} > \text{ORR (Letrozole)} + .10 \text{ data}] < 0.05$ . The comparative response rate for Letrozole alone is represented by a distribution of beta (136, 317), and a beta (0.60, 1.40) prior distribution is assumed for ORR of the experimental group. Maximum sample size is set at 45 patients.)

The first interim analysis will be conducted after the initial 15 patients have been evaluated for response. The trial will continue to accrue another 15 patients if at least 4 responses have been observed. At the second interim analysis, the trial will continue to accrue to the maximum sample size only if at least 8 objective responses have been observed among 30 patients.

A simulation study evaluated the properties of these stopping rules under several possible scenarios:

True ORR rate	Probability of early termination
.20	.83
.30	.40
.35	.22
.40	.11
.45	.05
.50	.02

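### Section 8.3 denies partial response if any lesion grows by any amount and scores the fall on products of diameters, which contradicts the RECIST sum-of-longest-diameters basis set in 8.1 and 8.1.3

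*Combined protocol and SAP*

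**What the plan says.** Section 8.1 adopts RECIST and explains: "Changes in only the largest diameter (unidimensional measurement) of the tumor lesions are used in the RECIST criteria". Section 8.1.3 defines target lesions as "All measurable lesions up to a maximum of five lesions per organ and 10 lesions in total", sums their longest diameters, and states: "The baseline sum LD will be used as reference by which to characterize the objective tumor response".

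Section 8.3 defines partial response differently. The threshold is a "30% or greater decrease in the sum of the products of diameters of all measured lesions", confirmed about four weeks later. It then adds: "No lesion may increase in size and no new lesion may appear". No minimum increase is given. The text does not say whether the comparison is with baseline, the smallest earlier value or the previous scan. In the same section, progression needs an increase of at least 25%, and growth below that is No Change.

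Minor response (MR) is "A measurable decrease in measurable lesion(s), which is too small or too brief to qualify as a Partial Response", and "MR is considered a failure, but should be noted as a possible signal of biologic activity".

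Section 13.0 counts objective responses at two futility looks. At the first, "The trial will continue to accrue another 15 patients if at least 4 responses have been observed"; at the second, at least 8 of 30 are needed. The comparison rate for letrozole alone is 136 of 453 (30%).

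**The concern.** Two parts of the primary-endpoint definition disagree. Sections 8.1 and 8.1.3 judge response on a sum of longest diameters. Section 8.3 judges it on a sum of products and lets a single lesion override that sum, however small its increase. An assessor cannot satisfy both.

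The no-increase clause has no allowance for reading error, although 8.1.1 admits lesions from 10 mm and 8.2 specifies CT cuts of 7 or 7.5 mm. Because response must be confirmed, the clause has to be met on both scans. The more lesions are followed, the more chances there are for one to read larger, so two patients with the same total shrinkage can be scored differently because of their lesion counts.

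A patient whose sum has fallen enough, with one lesion slightly larger, also has no clear category. Her fall is neither too small nor too brief for PR, and growth under 25% is not progression. ORR is the primary endpoint and drives both stopping counts, so what counts as a response needs to be unambiguous.

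**Working it through.** **1. The plan's stopping table.** Inputs from 13.0: stop if fewer than 4 of 15 or fewer than 8 of 30 respond. With X and Y independent Binomial(15, p),

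P(stop) = P(X ≤ 3) + Σ(x = 4 to 7) P(X = x) · P(Y ≤ 7 − x).

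| True ORR | Plan | Exact |
|---|---|---|
| 0.20 | .83 | 0.819 |
| 0.30 | .40 | 0.394 |
| 0.35 | .22 | 0.220 |
| 0.40 | .11 | 0.108 |
| 0.45 | .05 | 0.048 |
| 0.50 | .02 | 0.019 |

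The table is reproduced within 0.02. The Bayesian rule also gives these boundaries: the posterior probability of exceeding letrozole by 0.10 is 0.043 at 3/15 and 0.122 at 4/15, then 0.026 at 7/30 and 0.059 at 8/30, against the 0.05 cut-off.

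**2. The two metrics.** If both diameters shrink equally, a 30% fall in the product is a fall of 1 − √0.70 = 16% in each diameter. The threshold written in 8.3 is therefore looser than 30% on sum LD. Likewise, a 25% rise in the product is √1.25 − 1 = 12% in diameter.

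**3. Direction of the clause alone.** It adds a condition to PR. With everything else fixed, the number of responders can only fall or stay the same.

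**4. Size of the clause alone.** The documents give no reading error, between-lesion variation or distribution of lesion counts, so these are assumptions: fall measured on sum LD, comparison with baseline, error of 5-10% per measurement, between-lesion SD of log change 0.15-0.35, and both follow-up scans meeting 30%. Simulated share of such responses voided:

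| Target lesions | Voided |
|---|---|
| 1 | 0% |
| 3 | about 0-10% |
| 5 | about 1-23% |

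The zero for one lesion is a matter of logic: a lesion cannot be 30% smaller and also larger than at baseline. Part of the loss is real growth. With five lesions, error 5% and SD 0.35, about 20% were voided, but in only about 6% was no lesion truly larger.

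**5. Clause and metric together.** A separate simulation took error 10% and between-lesion SD 0.2 as a middle case.

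| Lesions | Voided, sum LD (noise alone) | Voided, products (noise alone) | Response rate, 8.3 as written | Response rate, sum LD without clause |
|---|---|---|---|---|
| 3 | 2.4% (1.9%) | 10.8% (6.7%) | 0.457 | 0.363 |
| 5 | 5.8% (4.6%) | 19.4% (11.6%) | 0.413 | 0.354 |
| 10 | 14.1% (11.1%) | 34.1% (18.4%) | 0.337 | 0.361 |

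The looser threshold outweighs the clause with three or five lesions, and the order reverses with ten.

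**6. What a loss would do to stopping.** If a share f of responses is voided at ORR 0.40, the counted rate is 0.40 × (1 − f):

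| f | Counted ORR | P(stop) |
|---|---|---|
| 0 | 0.400 | 0.108 |
| 2% | 0.392 | 0.122 |
| 5% | 0.380 | 0.146 |
| 10% | 0.360 | 0.192 |

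These are illustrations; the documents supply no value for f.

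**7. The reference scan matters.** If the comparison were with the previous scan, a lesion truly unchanged between the response and confirming scans would read larger about half the time (symmetric error, no rounding). Even patients with one lesion could then lose a response.

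**The case against.** A reader might infer that the clause biases ORR downward and that measurement noise is the main cause. The documents do not support either step. The rule as written also has a looser threshold, which pushes the response rate up, and in the middle case with three lesions it counts more responders than sum LD without the clause. Bias against the benchmark would also require the 136/453 to have been scored by a laxer rule, and its criteria are not stated. Where between-lesion variation is high, much of the voiding is true growth, and excluding such mixed responses is a legitimate purpose of a no-growth clause.

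A reader might also infer that the stopping table is wrong. It is indexed by true ORR; if that means response as 8.3 defines it, the table stands. Losses as large as 20%, which would take early termination to 0.317, need five or more lesions with sum LD and values near the top of the assumed ranges. Entry requires only one measurable lesion.

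Finally, MR is the likely home for a patient with one slightly larger lesion, so it goes too far to say she cannot be classified. She is a non-responder either way.

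All of this limits the size and direction of the effect. It does not remove the contradiction between 8.3 and 8.1 with 8.1.3, the missing reference scan, or the dependence on lesion count. Nor do the opposing effects cancel reliably: their balance changes sign with the number of lesions. If only the product wording were corrected, the clause would remain with nothing to offset it.

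**Conclusion.** The point holds as a documented contradiction in the primary endpoint. Section 8.3 uses a different metric from 8.1 and 8.1.3 and adds a zero-tolerance condition on single lesions without naming a reference scan. Relative to an otherwise identical rule, the clause can only remove responders, increasingly so with more target lesions. On sum LD the loss is nil with one lesion, small with three and potentially material with five or more. These sizes rest on assumed reading error and between-lesion variation and on a comparison with baseline, which is the natural reading of 8.1.3 but is not stated in 8.3. The net effect of 8.3 as written on ORR, and so on the chance of early termination, cannot be signed from the documents.

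**What to change.** Amend 8.3 to agree with 8.1 and 8.1.3:

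- Define the target-lesion part of PR as a confirmed decrease of at least 30% in the sum of longest diameters against the baseline sum LD, with no new lesion and no finding that meets the progression definition.
- Drop the no-increase clause for target lesions. If the sponsor wishes to keep a single-lesion condition, name the reference scan and state a tolerance.
- Express the progression definition on the same unidimensional metric, so that PR and progression can be applied together. That definition also triggers treatment discontinuation under 5.3 and 11.1, so those passages must be reconciled with it; no threshold is proposed here.

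The cost is a short amendment to 8.3, with no added scans or patients. Two downsides should be stated openly. Some mixed responses whose sum qualifies will count as PR. Moving from products to sum LD may also lower the counted ORR in patients with few lesions (0.457 to 0.363 in the three-lesion middle case), so the amendment should not be presented as one that raises the response rate.

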# **7.0 Conduct of the Study**

## **7.1 Visit Schedule**

- 7.1.1 Baseline laboratory must be done within 14 days of study entry.
- 7.1.1 Baseline imaging studies must be done within 4 weeks of study entry.
- 7.1.3 Baseline imaging studies will include computed tomography of chest and abdomen and bone scan (correlating bone X-rays is required if bone scan is positive), or PET scan.
- 7.1.4 Baseline laboratory studies will include a complete blood count, electrolytes, liver functions, tumor markers (CEA and CA 27.29), creatinine.

7.1.5 Laboratory tests: Week 1 2, 3, 4, 6, 8: Complete blood count, liver, electrolytes and creatinin. These laboratory tests will be performed monthly thereafter.

7.1.6 Clinic visits with physical exam: Baseline, months 1, 2, 4, 6, 9, 12 (Tumor markers (CEA and CA 27.29) will be drawn during these visits.

7.1.7 Radiologic imaging/restaging: Months 2, 4, 6, 9, 12 : Affected area will be evaluated. Patients with stable or responsive disease will be followed every 3 months thereafter.

7.1.8 Correlative studies: Serum for angiogenic molecules and cytokines including: serum vascular endothelial growth factor (sVEGF), basic fibroblast growth factor (bFGF), Interleukine-8 (IL-8), platelet-derived growth factor (PDGF), E-selectin, tumor-necrosis factor- $\alpha$  (TNF- $\alpha$ ), tumor-necrosis factor- $\beta$  (TNF- $\beta$ ), IGF-II and IGFBP-3 and proteomic analysis: Baseline and months 2 and 4.

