### 8.2 Guidelines for Evaluation of Measurable Disease

The same method of assessment and the same technique should be used to characterize each identified and reported lesion at baseline and during follow-up. Imaging-based evaluation is preferred to evaluation by clinical examination when both methods have been used to assess the antitumor effect of a treatment.

**Clinical lesions.** Clinical lesions will only be considered measurable when they are superficial (e.g., skin nodules and palpable lymph nodes). In the case of skin lesions, documentation by color photography, including a ruler to estimate the size of the lesion, is recommended.

**Chest x-ray.** Lesions on chest x-ray are acceptable as measurable lesions when they are clearly defined and surrounded by aerated lung. However, CT is preferable.

**Spiral CT and MRI.** For CT, cuts of 7 or 7.5 mm slice thickness (contiguously), for MR 6-10 mm slice thickness should be used. This applies to tumors of the chest, abdomen, and pelvis. Head and neck tumors and those of extremities usually require specific protocols.

**Ultrasound (US).** When the primary endpoint of the study is objective response evaluation, US should not be used to measure tumor lesions. It is, however, a possible alternative to clinical measurements of superficial palpable lymph nodes, subcutaneous lesions, and thyroid nodules. US might also be useful to confirm the complete disappearance of superficial lesions usually assessed by clinical examination.

**Tumor markers.** Tumor markers alone cannot be used to assess response. If markers are initially above the upper normal limit, they must normalize for a patient to be considered in complete clinical response.

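### The partial-response definition requires marker improvement with no baseline condition, so on a literal reading patients with normal markers at entry have no stated route to PR and the primary response rate may be biased down

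*Combined protocol and SAP*

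**What the plan says.** Section 8.1 adopts RECIST and states that "Changes in only the largest diameter (unidimensional measurement) of the tumor lesions are used in the RECIST criteria".

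Section 8.3 then adds marker conditions to both response categories. For CR the text is "Markers must be normal". For PR it is "Markers must have improved". The PR sentence has no baseline qualifier and does not say what counts as improvement, or whether both markers must show it.

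Section 8.2 limits the role of markers ("Tumor markers alone cannot be used to assess response") and gives the only rule that depends on the baseline value: "If markers are initially above the upper normal limit, they must normalize for a patient to be considered in complete clinical response". That rule covers CR only.

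The baseline laboratory panel in section 7.1 includes "tumor markers (CEA and CA 27.29), creatinine". None of the criteria in sections 3.2.1 and 3.2.2 requires either marker to be raised.

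Response rate is the efficacy measure in objective 1 and drives the stopping rule in section 13.0. At the first look, "The trial will continue to accrue another 15 patients if at least 4 responses have been observed". At the second, at least 8 responses among 30 patients are needed.

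**The concern.** Patients whose CEA and CA 27.29 are both normal can enroll, and their markers have nothing abnormal to improve. Applied as written, the PR sentence produces an odd ordering: such a patient satisfies the marker test for CR, the better response, and has no stated way to satisfy it for PR, the lesser one.

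A marker-normal patient with a confirmed, lasting shrinkage well beyond 30% would then fit no category in section 8.3. She is not a minor response, because that category is reserved for decreases insufficient in size or duration. She is not no change, and she is not progressive disease. Being neither CR nor PR, she drops out of the ORR numerator. A patient with one raised and one normal marker cannot be classified from the text either.

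The same count decides the primary estimate and whether the trial stops after 15 or 30 patients. With thresholds this low, one or two reclassified patients can decide whether accrual continues.

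**Working it through.** **Inputs from section 13.0.** Stop if 3 or fewer responses in 15, or 7 or fewer in 30; maximum 45 patients; target ORR 0.40; beta(136, 317) for letrozole alone; beta(0.60, 1.40) prior for the combination; margin 0.10; probability cutoff 0.05.

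**Inputs not in the documents (assumed).** f is the share of would-be PRs rejected because markers were normal at baseline, taken as 0 to 40%. If response is unrelated to marker status and the clause is applied strictly, f equals the share of patients who are marker-normal. c is the share of responders who are CR, taken as 0 or 25%.

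**Step 1: reproduce the plan's boundaries.** Integrating Pr[ORR(combination) > ORR(letrozole) + 0.10] over the two beta distributions gives 0.043 at 3/15 and 0.122 at 4/15, then 0.026 at 7/30 and 0.059 at 8/30. Against the 0.05 cutoff, the stated thresholds of 4 and 8 are correct.

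**Step 2: reproduce the plan's stopping probabilities.** With X the responses in the first 15 patients and Y those in the next 15,

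P(stop) = P(X ≤ 3) + Σ over x = 4 to 7 of P(X = x) · P(Y ≤ 7 − x).

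At ORR 0.40 this is 0.0905 + 0.0177 = 0.108.

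| True ORR | Plan | Exact |
|---|---|---|
| 0.20 | .83 | 0.819 |
| 0.30 | .40 | 0.393 |
| 0.35 | .22 | 0.220 |
| 0.40 | .11 | 0.108 |
| 0.45 | .05 | 0.048 |
| 0.50 | .02 | 0.019 |

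The design figures are sound. What is in question is the response rate that feeds them.

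**Step 3: effect of the PR clause under strict application.** A marker-normal patient can still be a CR, so only PRs are lost:

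recorded ORR = true ORR × [c + (1 − c)(1 − f)].

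For example, with f = 20% and c = 0, 0.40 × 0.80 = 0.32. With c = 25%, 0.40 × (0.25 + 0.75 × 0.80) = 0.34. Putting each recorded ORR into the Step 2 formula at a true ORR of 0.40 gives:

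| f | Recorded ORR, c = 0 | P(stop) | Recorded ORR, c = 25% | P(stop) |
|---|---|---|---|---|
| 0% | 0.40 | 0.11 | 0.40 | 0.11 |
| 10% | 0.36 | 0.19 | 0.37 | 0.17 |
| 20% | 0.32 | 0.32 | 0.34 | 0.25 |
| 30% | 0.28 | 0.48 | 0.31 | 0.35 |
| 40% | 0.24 | 0.66 | 0.28 | 0.48 |

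The row f = 0% is also the result if every assessor applies the clause only to markers that were raised at baseline.

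**The case against.** The strongest objection is that the literal reading is not the natural one. The sentence just before the marker condition, "Bone lesions must have improved by scan and shown some reossification by x-ray", also omits any words such as 'if present'. Taken literally, it would bar every patient without bone disease from PR. An assessor who supplies the missing condition there would probably supply it for markers too, and section 8.2 already reasons that way for CR. Because improvement is undefined, a fall within the normal range is not excluded either. This stands: a reader might infer that marker-normal patients can never be partial responders and that ORR is biased down, but the documents do not support either as a certainty. What remains is that two assessors can classify the same patient differently on the primary endpoint. Counting variation within the normal range as improvement would also make PR partly arbitrary.

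A second objection is that the net direction of error in ORR is not settled. The same PR definition uses a sum of products of diameters, whereas section 8.1 uses one dimension. For equal shrinkage in two diameters, a 30% fall in the product is only a 1 − √0.7 = 16% fall in diameter, which loosens PR. This also stands. The marker clause on its own can only lower the recorded rate, but it is not the only departure from section 8.1.

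Third, a reader might infer that the comparison with letrozole alone is tilted against the combination. Section 2.2.1 describes the historical 30% only as complete plus partial response and gives no criteria. Whether a marker condition applied there is unknown, so a differential bias is not shown.

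**Conclusion.** The concern holds as a defect in the primary endpoint definition. As written, the PR marker clause lacks the baseline condition that section 8.2 gives for CR and sits poorly with the diameter-based assessment in section 8.1. Strict application would remove real responders from ORR and from both interim counts.

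The effect is possible rather than established. At a true ORR of 0.40 it ranges from none, under the lenient reading, to a recorded ORR of 0.24 and an early-stopping probability of 0.66 (recorded 0.28 and stopping 0.48 if 25% of responders are CR). The upper end assumes strict application by every assessor, response unrelated to marker status and 40% of patients marker-normal. The documents give neither the marker-normal share nor the CR share. Even at a 10% share, strict application takes the chance of stopping a regimen that meets its target from 0.11 to between 0.17 and 0.19.

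**What to change.** Amend the PR definition in section 8.3 in one of two ways:

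- Remove the marker condition, so that PR rests on tumor measurements as section 8.1 states.
- Keep the existing requirement of improvement, but limit it to a marker above the upper normal limit at baseline. Define improvement, say what happens when only one of the two markers was raised, and state that markers normal at baseline do not affect PR.

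The second option should not weaken the requirement for patients whose markers were raised, since the defect does not concern them. Whichever is chosen, apply the same rule at the 15- and 30-patient looks and in the final analysis, and settle it before responses are classified.

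The cost is a short edit to one definition. The sample size, thresholds and stopping table do not change. The small downside is a PR slightly less stringent than the literal text.

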## **11.0 Patient Withdrawal From Study**

- 11.1 Evidence of disease progression
- 11.2 Development of a DLT that does not resolve within 2 weeks of stopping therapy.

- 11.3 Intercurrent illness which prevents further therapy  
General or specific changes in the patients condition which render the patient unacceptable for further treatment in the judgment of the investigator.
- 11.4 Protocol violation (including non-compliance).  
The patient or physician are free to discontinue treatment at any time if it is believed to be in the best interest of the patient.

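### Section 8.3 lets one lesion's growth count as progression, in conflict with 8.1 and 8.1.3; in multi-lesion patients this biases time to progression downward

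*Combined protocol and SAP*

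**What the plan says.** Section 8.1 adopts RECIST and states the unit of measurement: "Changes in only the largest diameter (unidimensional measurement) of the tumor lesions are used in the RECIST criteria".

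Section 8.1.3 defines the target lesions ("All measurable lesions up to a maximum of five lesions per organ and 10 lesions in total") and one summary over them: "A sum of the longest diameter (LD) for all target lesions will be calculated and reported as the baseline sum LD". It then fixes the role of that summary: "The baseline sum LD will be used as reference by which to characterize the objective tumor response".

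Section 8.3 departs from this twice. Partial response is a "30% or greater decrease in the sum of the products of diameters of all measured lesions". Progression is a 25% or greater increase "in the sum of the products of diameters of any measurable lesion", or similar growth in non-measurable lesions, or an unequivocal new lesion.

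Section 8.3 has two partial safeguards. Progression should not be called before two cycles. A 50% increase between the first and second cycle counts without re-measurement, which implies that smaller increases are re-measured. The confirmation paragraph covers CR, PR and stable disease and does not mention progression.

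Progression is used elsewhere. Time to progression is the third objective in 1.0 and is reported under 13.0. "Evidence of disease progression" is the first withdrawal criterion in 11.0, and progression also ends treatment in 5.3.

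**The concern.** The change from all lesions (response) to any lesion (progression) within one section makes the single-lesion reading the natural one, but the word for a sum points the other way. Two readers can therefore classify the same scan differently.

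The choice matters because the two readings react to measurement error in opposite ways. If each lesion is tested separately, the chance that at least one crosses 25% rises with the number of lesions. In a sum, independent errors partly cancel. A false progression sets the progression date, so the single-lesion reading pulls time to progression downward, and more so in patients with more lesions.

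This is related to the conflict between products and longest diameters but is not the same fault. If 8.3 were reworded to longest diameters and still said any measurable lesion, the single-lesion trigger would remain.

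**Working it through.** **Inputs from the documents.** Threshold 25% (8.3); up to 10 target lesions (8.1.3); lesions measurable from 10 mm (8.1.1); restaging at months 2, 4, 6, 9 and 12 (7.1.7). The plan gives no measurement-error figure and no target for time to progression, so it has no figure of its own to reproduce on this point.

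**Assumptions.** Independent error on each diameter at baseline and follow-up, with a CV *c* of 5%, 8% or 10%; *k* = 3 or 5 equal lesions; no true change; baseline as reference, since 8.3 does not say.

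**1. Size of change needed.** √1.25 = 1.118, so a 25% rise in a product is 11.8% on each diameter, or about 1.2 mm on a 10 × 10 mm lesion.

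**2. The readings can disagree sharply.** On longest diameters, let 40, 30, 30 and 10 mm become 24, 18, 18 and 12.5 mm. The sum goes from 110 to 72.5 mm, and 72.5/110 = 0.659, a fall of 34%. The last lesion is up 25%, so a single-lesion rule calls progression.

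**3. Approximate formula.** A ratio of two products carries four independent errors, so its log has SD about 2*c*. With ln 1.25 = 0.2231:

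- Any of *k* lesions: 1 − Φ(0.2231/2*c*)^*k*. At *c* = 10%, Φ(1.116) = 0.868, giving 34.7% for *k* = 3 and 50.8% for *k* = 5.
- Sum over *k* equal lesions: the SD is about 2*c*/√*k*. At *c* = 10% and *k* = 3, 0.2231/0.1155 = 1.93, giving 2.7%.

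**4. Simulation, 200,000 unchanged patients per setting.** False progression per scan, range over *k* = 3 to 5:

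| Rule (25% threshold) | CV 5% | CV 8% | CV 10% |
|---|---|---|---|
| Any lesion, product | 4–6% | 23–35% | 35–51% |
| Same, and same lesion still ≥25% on one repeat | 0.7–1.1% | 8–13% | 15–24% |
| Sum of products | ≤0.01% | 0.1–0.8% | 0.7–2.7% |
| Any lesion, longest diameter | 0.3–0.4% | 7–12% | 17–26% |
| Sum of longest diameters | ≤0.4% | ≤0.4% | ≤0.4% |

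Repeat runs moved the largest entries to about 52% (any lesion, product) and 2.8% (sum of products).

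**5. A different error model.** With lesions of 10, 30 and 40 mm and a fixed error SD of 0.5, 1.0, 1.5 or 2.0 mm, the single-lesion product rule gives 1.3%, 13.5%, 24.3% or 33.5%. The total product gives at most 0.2%. Here the 10 mm lesion drives most of the false calls.

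**6. Does the trigger hit responders?** Take a patient exactly at the partial-response threshold, with the true product down 30%. The measured ratio must be off by 1.25/0.70 = 1.786, and ln 1.786 = 0.580. At *c* = 10%, 0.580/0.20 = 2.90, or about 0.2% per lesion. The simulation gives 0.0% at CV 5%, about 0.1% at 8%, and 0.7–1.2% at 10%. The separate partial-response condition that no lesion may grow at all needs an error of only 1/0.70 = 1.43. At CV 10% it fails 11–18% of these patients per scan.

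**The case against.** The strongest objection concerns consequences. A reader might infer that false progression also lowers ORR and pushes the looks at 15 and 30 patients towards stopping, because 13.0 counts removed patients as failures. As an arithmetic illustration, losing 10% of responders at a true ORR of .40 would raise early termination from .108 (.11 in the plan's table) to .192. The documents do not support that loss. Unchanged patients are not responders in the first place, and step 6 shows that patients at the response threshold meet the progression trigger in 0–1.2% of scans. The no-growth condition in partial response dominates. It already blocks a response at that scan for the patient in step 2, and changing the progression wording would leave it in place. A late responder wrongly removed at an early scan remains possible, but its frequency has not been estimated.

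Second, 8.3 has safeguards. The two-cycle minimum screens out little, because a cycle is four weeks and first restaging is at month 2. The implied repeat measurement would help materially (second row of the table), but it is not written as a rule for a 25% increase, and the rates with it still exceed those for the sum without it.

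Third, the text can be read as an aggregate, so it cannot be said that the plan deliberately chose a single-lesion rule. This stands: the fault is an unresolved inconsistency, with harm if the literal reading is followed.

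Fourth, the size depends on an assumed error. At CV 5% with longest diameters the single-lesion excess is only 0.3–0.4%. With one lesion the two readings coincide. Both limits stand.

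**Conclusion.** The point holds for time to progression in patients with several lesions. The progression definition in 8.3 is incoherent as written and conflicts with 8.1, with 8.1.3 and with the partial-response definition beside it. Followed literally, it inflates false progression per scan to about 4–6%, 23–35% or 35–51% at an assumed CV of 5%, 8% or 10%. With one repeat measurement the figures are about 1%, 8–13% or 15–24%. The same threshold on the sum of products gives at most about 2.7%.

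These rates rest on the assumed CV, independent errors, 3 to 5 equal lesions and baseline as reference. They are per scan and are not accumulated over the five scheduled restagings. The direction of the bias is firm; its size is not.

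No material effect on ORR or on the futility rule has been shown, and none should be claimed from this wording.

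**What to change.** Reconcile 8.1, 8.1.3 and 8.3 so that measurable-disease progression, as the event for time to progression, is defined on one stated quantity consistent with the sum of longest diameters over target lesions. Keep unequivocal new lesions as a separate trigger. State the reference point (baseline or smallest value) and whether a 25% increase needs a repeat measurement.

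Make the change together with the correction of products versus longest diameters, since the same sentences are affected. Progression also governs stopping treatment in 5.3 and withdrawal in 11.0. Those rules must be consistent with whatever is adopted, but their content is for the trial team.

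The cost is wording only, because 8.1.3 already requires the diameters and their baseline sum. The downside is small: true growth confined to one small lesion is called later unless it moves the sum.
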